5.4 Dose and Dosing Schedule

octaplasTM, ABO blood group specific, will be given as replacement fluid during TPE and administered per institutional standard of care. It will be used in lieu of FFP during the treatment period.

The total octaplasTM volume infused and time details of each infusion episode will be recorded.

Patients will be followed for one week (7 days) during their therapy which could consist of one or more TPE procedures. The recommended dose is a total plasma volume between 40 to 60 mL/kg, as prescribed by the treating physician. The dosing regimen might differ from the general recommendation, depending on the therapeutic treatment plan and the investigator's evaluation of the respective clinical situation (e.g. plasma exchange). The infusion rate of octaplasTM should not exceed 0.020-0.025 mmol/kg BW (body weight)/min, which is equal to <1 mL/kg BW/min.

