5.5 Preparation and Method of Administration

octaplasTM will be used per the approved labeling for the product (see **Appendix 1**). octaplasTM will be administered based on ABO-blood group specificity. In urgent cases, or in circumstances that no same blood group is available (type A octaplasTM for type A recipient), the patient can be administered octaplasTM that is compatible to the recipient's blood group (e.g. type AB octaplasTM can be administered to a type A recipient).

All attempts should be made to ensure adequate octaplasTM blood-type specific inventory is available to meet patient orders. Shipment requests to Octapharma should coincide to meet these needs and should be issued promptly, taking into consideration processing and shipment time.

During the study treatment period, the hierarchy of plasma choice is:

- 1. octaplas™ blood group specific
- 2. octaplasTM blood group compatible
- 3. FFP

Further, if plasma is needed during the TPE follow-up period, octaplasTM should be administered.

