3.2. Study Endpoints (Target Variables)

3.2.1. Primary Endpoint

The primary endpoint is the monitoring of SAEs, ADRs, TEs and TEEs caused by the octaplas™ used for therapeutic plasma exchange (TPE). All such events will be listed and the rate of such reactions per patient and per TPE procedure will be calculated, overall as well as for all relevant combinations of age groups and reaction characteristics.

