6.2. Premature Termination of the Study

If early termination of the study becomes necessary for whatever reason, the sponsor and the investigator will ensure that adequate consideration is given to the protection of the patients' interests. Such a premature termination will be communicated in accordance with applicable regulatory requirements. The Investigator will promptly inform the Independent Ethics Committee (IEC)/Institutional Review Board (IRB) and provide a detailed written explanation. The pertinent regulatory authorities will be informed according to national regulations.

7. Analysis Populations

The following populations will be considered for the statistical analysis:

The safety population (SAF) will include all patients who received at least one infusion of octaplas.

The full analysis set (FAS) is defined according to the intent-to-treat (ITT) principle and will include all patients of the SAF with any information available on the primary endpoint; these are all treated patients monitored for the above mentioned events (SAEs, ADRs etc.) after start of the TPE, and it is thus expected that this population will coincide with the SAF.

The per-protocol (PP) population will include all patients who have completed the infusion episode(s) and the final examination without major protocol deviations that would have an effect on the evaluation of the primary endpoint. Examples of protocol deviations to be considered in this respect would be violations of the study entry criteria, dosing errors, the use of prohibited concomitant medications, or the occurrence of completely unrelated medical events that require an interruption of the study procedures. The final decision regarding inclusion/exclusion of patients from the analysis sets will be taken by a panel including the Clinical Project Manager, the study statistician and a medical expert during a data review meeting before database lock. The decisions taken will be based on a review of complete data listings, and documented before the database is locked and the analysis is performed.

8. General Issues for Statistical Analysis

Descriptive summaries will be presented for each of the primary and secondary variables. In general, summaries will be completed for all patients overall and by age group. Continuous, quantitative variable summaries will include the number of patients with non-missing values (N), mean, standard deviation, median, minimum and maximum, 1st and 3rd quartile.

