9.4. Measurement of Treatment Compliance

The following parameters will be listed and/or summarized per patient and/or per infusion:

- Body weight
- Total volume (mL) of octaplas (blood group specific / blood group compatible) and FFP (if applicable) used per infusion episode and in total

- Actual dose (mL/kg) per infusion episode and in total (based on the latest available weight measurement for each TPE)
- Total number of infusions administered
- Total number of bags administered
- Infusion times and rates
- Overall amount of product administered and batches used (only included in data listings)

10. Efficacy Analysis

Efficacy will not be assessed.

16/21

11. Safety and Tolerability Analyses

To primary objective of LAS-213 is to assess safety and tolerability of octaplas in the pediatric population by monitoring SAEs, ADRs, TEs, TEEs, and by measuring safety laboratory parameters. This will be done by means of descriptive analyses of all safety related data available for the Safety Population.

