11.1. SAEs, ADRs, TEs, and TEEs

A Serious Adverse Event (SAE) is any untoward medical occurrence at any dose that

- results in death
- is life-threatening
- requires in-patient hospitalization or prolongation of existing hospitalization
- results in persistent or significant disability/incapacity
- is a congenital anomaly/birth defect
- is another important medical event

An Adverse Drug Reaction (ADR) in the context of this study is any noxious and unintended response to octaplas related to any dose; this means that a causal relationship between octaplas and the reported reaction cannot be ruled out, i.e. the relationship must be determined to be at least possibly related to administration of *octaplas* by the investigator or by Octapharma's medical expert or an adjudicator of the independent data monitoring committee (TEEs and TEs). Reactions with a missing or indeterminate causality assessment will also be classified as ADRs.

Serious Adverse Events (SAEs), Thrombotic events (TEs) and thromboembolic events (TEEs) will be handled in exactly the same fashion as ADRs in the context of the safety analysis. The only difference is that TEs and TEEs will be included in the analysis regardless of the causality assessment; even if such an event is reported as not related to study drug, it will be included in all data listings and tabulations. For the remainder of this section the term 'event' will thus be used to refer to any ADR, TE, or TEE.

All of the below will feature this classification (SAE, ADR, TE, TEE) as additional event characteristic if applicable.

All events for each patient, including multiple occurrences of the same reaction, will be listed in full detail, including reported term, MedDRA preferred term and system organ class, onset, duration, time to the event occurrence from last dose, causality, dosage, severity, seriousness and actions taken. The listing will include the number of the last infusion prior to each event and the relative time. An evaluation to identify any event with increased frequency over time will be performed.

For each age group and for the study as a whole the following will be given:

- Total number of events reported
- Number of events divided by the total number of TPEs

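### SAP 11.1 divides events by all TPEs, so any FFP-only TPE would dilute the per-TPE rate of octaplas-attributed ADRs (minor, and only if such TPEs occur)

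*SAP*

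**What the plan says.** SAP 3.2.1 ties the primary endpoint to SAEs, ADRs, TEs and TEEs caused by octaplas and states that "the rate of such reactions per patient and per TPE procedure will be calculated". SAP 11.1 gives the calculation for each age group and overall: "Number of events divided by the total number of TPEs". Nothing in either section restricts the TPEs by replacement fluid.

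FFP is allowed for. Protocol 5.5 introduces its ranking with "During the study treatment period, the hierarchy of plasma choice is" and lists group-specific octaplas, then group-compatible octaplas, then FFP. Protocol 5.4 makes clear that octaplas is the intended product: "It will be used in lieu of FFP during the treatment period". SAP 9.4 plans to list or summarize octaplas volume and "FFP (if applicable) used per infusion episode and in total".

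The analysis population is set at patient level. SAP 7 says: "The safety population (SAF) will include all patients who received at least one infusion of octaplas". There is no matching criterion for a TPE.

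On the numerator, SAP 11.1 defines an ADR as a response to octaplas that is at least possibly related. It adds two rules: "Reactions with a missing or indeterminate causality assessment will also be classified as ADRs", and "TEs and TEEs will be included in the analysis regardless of the causality assessment". It then defines the word event, for the rest of that section, as any ADR, TE or TEE.

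**The concern.** A rate of octaplas reactions per procedure should have procedures with octaplas exposure underneath it. Suppose a patient has one octaplas TPE and later an FFP-only TPE. The patient is in the safety population, and both TPEs count in the denominator, although the second is not an octaplas exposure. Each such TPE lowers the apparent rate of octaplas-attributed ADRs.

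This is one of the two forms of rate named for the primary endpoint, in a post-marketing requirement study whose appended label says pediatric safety has not been evaluated. An understated ADR rate is the unfavorable direction for a safety study. Because the rate is also given by age group, uneven FFP use between age groups could make them look different when their rates per octaplas TPE are equal.

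**Working it through.** **The plan's own figure.** There is none to reproduce. The documents give no expected number of TPEs, event rate or FFP share, and the minimum of 40 patients is not based on power. Apart from the 40 patients, every input below is an assumption.

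**Step 1: octaplas-attributed ADRs.** Let x be the number of ADRs attributed to octaplas, T_oct the TPEs with any octaplas, T_FFP the FFP-only TPEs, and q = T_FFP / (T_oct + T_FFP).

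- Planned rate = x / (T_oct + T_FFP)
- Rate per octaplas TPE = x / T_oct
- Planned rate divided by rate per octaplas TPE = 1 − q

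Assume 40 patients × 5 TPEs = 200 TPEs and x = 8. The planned rate is 8/200 = 4.00% (exact 95% CI 1.74% to 7.73%, ignoring clustering within patient).

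| q | FFP-only TPEs | Rate per octaplas TPE | Factor 1/(1 − q) |
|---|---|---|---|
| 0% | 0 | 8/200 = 4.00% | 1.000 |
| 1% | 2 | 8/198 = 4.04% | 1.010 |
| 5% | 10 | 8/190 = 4.21% | 1.053 |
| 10% | 20 | 8/180 = 4.44% | 1.111 |

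The factor does not depend on the number of TPEs per patient. With 40 × 3 = 120 TPEs and 10 ADRs, the planned rate is 10/120 = 8.3% (exact Poisson 95% CI 4.0% to 15.3%). Per octaplas TPE it is 10/114 = 8.8% at q = 5%, 10/108 = 9.3% at q = 10% and 10/96 = 10.4% at q = 20%.

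**Step 2: events that can be counted after an FFP-only TPE.** TEs and TEEs count whatever their cause, and reactions with missing causality count as ADRs. If counted events occur at rate r per octaplas TPE and s per FFP-only TPE, the planned rate is (1 − q)r + qs. With q = 10% and r = 10%:

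- s = 0%: 9.0%
- s = 5%: 9.5%
- s = 10%: 10.0%
- s = 15%: 10.5%

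The planned rate is too low only when s is below r. For these events the direction is open.

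**Step 3: changing the denominator alone is not enough.** Take q = 5% of 200 TPEs (10 FFP-only), 8 ADRs and 2 TEs, with one TE after an FFP-only TPE.

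- Planned: 10/200 = 5.00%
- Denominator changed, numerator unchanged: 10/190 = 5.26%
- Numerator and denominator matched: 9/190 = 4.74%

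**Step 4: tying every event to the last TPE goes too far.** Suppose one of the 8 octaplas-attributed ADRs starts after an FFP-only TPE.

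- Last-TPE rule applied to all events: 7/190 = 3.68%, below the planned 4.00%
- All attributed ADRs kept: 8/190 = 4.21%

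An ADR attributed to octaplas therefore has to stay in the numerator whichever TPE came last.

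**Step 5: per-patient rates.** Every patient in the safety population has received octaplas, so no patient without octaplas exposure enters that denominator. These rates are not diluted in this way.

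**The case against.** The strongest reply is that FFP-only TPEs are an inference. No section describes one, and the FFP entry in SAP 9.4 fits a mixed exchange equally well. Octaplas is first and second choice, protocol 5.5 asks sites to hold enough inventory, and protocol 5.7.2 expects full compliance. The study is descriptive, no test depends on this rate, and the shifts in the worked examples lie inside the confidence intervals.

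The plan also makes FFP use visible. Volumes are reported per episode, each event is listed with the last infusion before it, and patient profiles show all treatment details. Other plasma products are relevant concomitant medications (protocol 4.2), and SAP 5.2 names such medications among the characteristics to be examined.

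Most of this stands, and it limits the point to a small and conditional one. It does not remove it. The protocol permits FFP during the treatment period, the stated denominator is unqualified, and listings let a reader see FFP use without correcting the rate.

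A reader might also infer that unrelated SAEs after FFP enter this rate. The documents do not establish that. SAP 11.1 says SAEs are handled like ADRs, but it waives the causality requirement only for TEs and TEEs, and its definition of an event names ADRs, TEs and TEEs.

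**Conclusion.** The point holds as a minor one. If any FFP-only TPE occurs in a treated patient, the planned per-TPE rate of octaplas-attributed ADRs equals the rate per octaplas TPE multiplied by (1 − q). That is a relative understatement of 5% at q = 5% and 10% at q = 10%. If q = 0 there is no effect.

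A reader might infer that the whole per-TPE rate is biased downward. The documents do not support that, because TEs, TEEs and reactions with missing causality can be counted after an FFP-only TPE and can move the rate either way. Nor is there ground to say that the study's conclusions would change. The size rests on q, which the documents do not give and which is probably small because FFP is the last choice.

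**What to change.** In SAP 3.2.1 and 11.1, before database lock:

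- **Denominator.** Report the per-TPE rate over TPEs in which any octaplas was infused. A mixed octaplas/FFP TPE counts as an octaplas TPE.
- **ADRs.** Keep every ADR assessed as at least possibly related to octaplas in the numerator, whichever TPE came last.
- **TEs, TEEs and reactions with missing causality.** Count those whose last TPE included octaplas. List those after an FFP-only TPE separately, with time since the last octaplas infusion.
- **Second line.** Keep the rate of all events over all TPEs, and state the number of FFP-only TPEs. If that number is zero, the two lines agree.

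The cost is one redefined rate, one flag per TPE (octaplas volume above zero) and one link from event to TPE. Volumes and TPE times are already recorded (SAP 4.1 and 9.4), the event listing already carries the last prior infusion, and the table list is still to be supplied (SAP 13). No new data and no protocol amendment are needed.

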12.1. General Reporting Conventions

- All tables and data listings will be developed in landscape orientation, unless presented as part of the text in a CSR.
- Figures will in general also be presented in landscape orientation, unless presented as part of the text in a CSR. Exceptions are the Trellis plots that might be presented in portrait orientation.
- Legends will be used for all figures with more than one variable or item displayed.
- Figures will be in black and white, unless color figures have been identified as useful for discriminating presentation in the figure. Lines in figures should be wide enough to view the line after being photocopied.
- Specialized text styles, such as bolding, italics, borders, shading, superscripted and subscripted text will not be used in tables, figures and data listings unless they add significant value to the table, figure, or data listing.
- Only standard keyboard characters should be used in tables and data listings. Special characters, such as non-printable control characters, printer specific, or font specific characters, will not be used on a table, figure, or data listing. Hexadecimal character representations are allowed (e.g., μ, α, β).
- The ICH numbering convention is to be used for all tables, figures and data listings.
- All footnotes will be left justified and placed at the bottom of a page. Footnotes must be
 present on the page where they are first referenced. Footnotes should be used sparingly
 and must add value to the table, figure, or data listing. If more than four footnote lines are
 planned then a cover page may be used to display footnotes.
- Missing values for both numeric and character variables will be presented as blanks in a table or data listing. A zero (0) may be used if appropriate to identify when the frequency of a variable is not observed.
- All date values will be presented as DDMMMYYYY (e.g., 29AUG2001) format.
- All observed time values will be presented using a 24-hour clock HH:MM format (e.g. 15:26).
- Time durations will be reported in HH:MM notation. The use of decimal notation to present (display) time durations should be avoided (e.g. 0.083h = 5min) unless it is necessary to show the computation of time differences in a table, figure, or data listing, in which case both notations may be used to display the time duration.
- All tables, figures and data listings will have the name of the program, and a date stamp on the bottom of each output.

12.2. Population Summary Conventions

 Population(s) represented on the tables or data listings will be clearly identified in the title as "Population: <name of population>" where <name of population> is any of the analysis

- population names or abbreviations defined in section 7 (safety analysis set (SAF), full analysis set (FAS or ITT), per-protocol set (PP)).
- Sub-population(s) or special population(s) descriptions will provide sufficient detail to ensure comprehension of the population (e.g., ITT Females, Per-Protocol Males with Hemolytic uremic syndrome) used for analysis in a table or figure.
- Population sizes may be presented for each treatment or dosing category as totals in the column header as (N=xxx), where appropriate.
- Population sizes shown with summary statistics are the samples sizes (n) of patients with non-missing values.
- All population summaries for continuous variables will include: N, mean, SD, median, Q1, Q3, minimum and maximum.
- All percentages are rounded and reported to a single decimal point (xx.x%).

13. Tables, Listings and Figures

To be supplied in a separate document later when all feedback from authorities will be available.
